### **PRIMARY ANALYSIS OF THE PRIMARY EFFICACY CRITERION**

The primary analysis of the primary efficacy criterion will correspond to the primary objective of the study, which is to evaluate a strategy of COPD management to reduce the average yearly duration of unscheduled hospitalisations whatever their reason, in patients with GOLD III/IV COPD.

In order to deal with patients followed-up over different duration, their individual recorded cumulated number of unscheduled hospital days whatever their reason ( $D_i$  expressed in days, as recorded by the investigators) will be normalised on a yearly basis, by multiplying  $D_i$  by the ratio [365 days / total number of days of the patient's *Follow-Up Period*] and rounding it at the nearest integer. Thus, a patient for whom 18 unscheduled hospital days have been recorded over a 6-month (182 days) follow-up prior to study premature withdrawal will be analysed as having experienced a yearly estimated duration of hospitalisation of [18 x (365/182)] ~ 36 days. In the same manner, a patient for whom 18 unscheduled hospital days have been recorded over a 2-year (731 days) follow-up will be analysed as having experienced a yearly estimated duration of hospitalisation of [18 x (365/731)] ~ 9 days.

On the ITT data set (*defined in section 7.B.3.1*), the normalised individual yearly duration of unscheduled hospitalisations whatever their reason will be considered as categorical data (0, 1, 2, 3, 4, ... days) and compared between the 2 study groups using the Wilcoxon's rank sum test, in all investigational centres and countries pooled together.

This non-parametric test is commonly used to test that the multinomial distributions of an ordinal categorical parameter are the same across 2 independent samples.

The null hypothesis of interest  $H_0$  is that the distribution of the normalised individual yearly duration of unscheduled hospitalisations whatever their reason in the Intervention group is equal to the one observed in the Control group. The alternative 2-sided hypothesis  $H_1$  is that the distribution of the normalised individual yearly duration of unscheduled hospitalisations whatever their reason in the Intervention group is different from the one observed in the Control group.

If  $F_{\text{Intervention}}$  denotes the multinomial distribution of the normalised individual yearly duration of unscheduled hospitalisations whatever their reason in the Intervention group and  $F_{\text{Control}}$  the multinomial distribution of this primary efficacy criterion in the Control group, the Wilcoxon's rank sum statistic tests:

$$\begin{array}{ll} H_0: & F_{\text{Intervention}} = F_{\text{Control}} \\ \text{against } H_1: & F_{\text{Intervention}} \neq F_{\text{Control}}. \end{array}$$

## **SUPPORTIVE ANALYSES OF THE PRIMARY EFFICACY CRITERION**

The primary analysis of the primary efficacy criterion will be repeated in a descriptive and exploratory manner in each of the 4 participating countries where the number of randomised patients allows the performance of this analysis separately.

Moreover, if it appears necessary to define a secondary PP data set (*defined in section 7.B.3.1*), the robustness of the results of the primary analysis of the primary efficacy criterion will be checked by repeating it on the PP data set, first, globally with all countries pooled together and in a second step, in each of the 4 participating countries where the number of randomised patients allows the performance of this analysis separately.

## **ADDITIONAL ANALYSES OF THE PRIMARY EFFICACY CRITERION**

To further explore the primary criterion, a parametric analysis of variance of the primary efficacy criterion will be performed on the ITT data set including three (3) factors: study group and country effects, as well as their interaction.

The primary analysis of the primary efficacy criterion and its supportive analyses will be repeated on the duration of unscheduled hospitalisations whatever their reason, confirmed in a blind manner by the members of the EVC (*see section 6.D*).

An exploratory multiple-factor regression analysis will also be performed to identify the independent predictors of the primary efficacy criterion. The statistical model building will follow the principle of seeking the most parsimonious model which still explains the data. The clinically relevant factors which will be investigated will be:

- study group,
- gender,
- age classified in the six (6) categories pre-defined in the Charlson Comorbidity Index (*i.e.*, < 50, [50 ; 60[, [60 ; 70[, [70 ; 80[, [80 ; 90[ and [90 ; 100[ years old),
- smoking status at Visit 1,
- need for respiratory assistance (*i.e.* oxygen and/or home Non-Invasive Ventilation (NIV) at Selection (Visit 0),
- need for Continuous Positive Airway Pressure (CPAP) at Selection (Visit 0)),
- need for respiratory assistance (*i.e.*, oxygen therapy and/or home Non-Invasive Ventilation (NIV)) at Selection (Visit 0) and/or during the study participation,
- need for Continuous Positive Airway Pressure (CPAP) at Selection (Visit 0) and/or during the study participation,
- need for continuous Long Term Oxygen Therapy (*i.e.*, daily oxygen duration prescribed of 15 hours or more) at Selection (Visit 0) and/or during the study participation,
- experience of at least 2 moderate or severe COPD exacerbations during the *Follow-Up Period* as recorded by the investigators,
- baseline FEV1 value (*expressed as percentage of predicted value*) classified in the four (4) categories pre-defined in the BODE index (*i.e.*, ≤ 35, ]35 ; 50[, [50 ; 65[ and ≥ 65%),
- Body Mass Index (BMI) at Selection classified in the two (2) categories pre-defined in the BODE index (*i.e.*, ≤ 21 and > 21 kg/m^2),
- baseline BODE index classified in the four (4) categories mentioned in section 6.A.2.6 (*i.e.*, [0 ; 2], [3 ; 4], [5 ; 6] and [7 ; 10]),

- baseline Charlson Comorbidity Index (*which may be separated in a few appropriate categories prior to the exploratory research of its potential predictive role on the primary efficacy criterion*).

If the descriptive analysis of the comparability of study groups at Selection and/or during the *Run-In Period* reveals any random imbalance of clinical significance between both study groups (*as specified in section 7.B.3.2*), this list of a priori identified potentially predictive factors will be implemented accordingly.

To carry out the exploratory multiple-factor regression planned, the following analyses will be performed successively:

- in a first step, a two-factor regression analysis involving the study group and each of the investigated factor listed above separately, as well as their interaction will be performed. If some factors or their interaction appear to be predictive (*i.e., statistically significant at level  $\alpha = 0.10$* ) of the primary efficacy criterion, they will be gathered into a multiple-factor model in addition to the study group factor. Backward elimination at level  $\alpha = 0.10$  will then be applied for the model determination. Any factor remaining in the model will be considered an independent predictor,
- in a second step, an exploratory multiple-factor regression analysis involving the study group and all factors selected in the first step described above, including their interaction, if relevant, will be performed to identify the independent predictors of the primary efficacy criterion. Conclusions regarding the study group effect will be generalised if they apply to all subgroups based on other factors.

Goodness-of-fit (*i.e., predicted values are an accurate representation of the observed values*) of the final selected model will be investigated by providing summary measurements of the distance between observed and fitted values. Moreover, an analysis of the residuals of the final selected model will be performed (*using both Pearson's and deviance residuals*).

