#### **5.A.3 Oxygen sources**

Oxygen prescriptions to the study patients will follow the standard protocols of the investigational centres, and they will be at the investigator’s discretion throughout the study period.

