## **6.D ENDPOINT VALIDATION COMMITTEE**

An Endpoint Validation Committee (EVC) will be established to review in a blind manner all hospitalisations having been reported for each randomised patient during the *Follow-Up Period*. The major reason is that hospitalisation may be considered as a potentially biased outcome measure, because somewhat subjective, and physician- or centre-dependent, as health care availability, each physician's routine practice and social considerations can markedly influence the decision to hospitalise a patient.

The EVC will be composed of three (3) independent physicians with clinical and research expertise in COPD. The 3 members will be appointed by the sponsor (AIR LIQUIDE Santé INTERNATIONAL) but will not be involved in the study conduct.

The role of the EVC members will be to adjudicate the reason and appropriateness of all hospital admissions and, for hospitalisations due to COPD exacerbation, to check for the presence of recognised criteria for hospital admission as published in the GOLD 2008 guidelines. Adjudication rules will be defined by the EVC members and sponsor representatives before starting adjudication of cases.

To adjudicate all hospitalisations recorded, the EVC members will review all individual medical reports (*anonymous reports, blinded for study group allocation, and translated in English by the study Clinical Research Associates (CRAs)*) related to hospitalisations having occurred in randomised patients during the *Follow-Up Period*. The following will be adjudicated:

- Criteria for hospitalisation,
- Reason for hospitalisation: first attributing the hospitalisation to a specific cause, then distinguishing hospitalisations directly related to COPD and to other causes, then grouping them into general pathophysiological categories (*respiratory, cardiovascular, cancer or other*),
- Cause of prolonged hospitalisation (*defined by an overall duration of hospitalisation > 30 days*).

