### **7.B.2**     *Determination of sample size*

The primary objective of this phase IV study is to show that the set-up of the Home-Based Disease Management Program in patients with GOLD III/IV COPD reduces the individual yearly duration of unscheduled hospitalisations whatever their reason. Based on published results and assuming:

- an expected difference of 10 days of hospitalisation between the average individual yearly duration of unscheduled hospitalisation whatever their reason observed in the Intervention group and in the Control group,
- an estimated common standard deviation of 25 days,
- a type I error set to  $\alpha = 0.05$  (*two-sided conditions*),
- and  $(1-\beta)$  power equal to 0.90,

and using the nQuery Advisor® software Version 6.01 and the estimation provided for the Wilcoxon (*Mann-Whitney*) rank-sum test for a continuous outcome, the number of patients required is estimated to be 143 per study group.

With an expected 25.0% dropout rate per year over the *Follow-Up Period* (*i.e., at most 6.25% over the first 3 months (between Visit 1 and Visit 2) with no available individual data allowing the estimation of the primary efficacy criterion (as detailed in section 7.B.3.5) for the concerned patients*), this sample size estimation results in randomising around 306 patients, *i.e.,* approximately 153 patients in the Intervention group and 153 patients in the Control group.

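### The exploratory predictor regression for hospital days includes neither country nor centre, so a factor that only marks a site can be labelled an independent predictor

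*Protocol*

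**What the plan says.** In Protocol section 7.B.3.5, under the additional analyses of the primary criterion, two models of hospital days stand next to each other.

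- The first is an analysis of variance with "study group and country effects, as well as their interaction". It holds no patient-level factor.
- The second is introduced by "An exploratory multiple-factor regression analysis will also be performed to identify the independent predictors of the primary efficacy criterion". Its list has 14 entries: study group, gender, age, smoking, four entries on respiratory assistance and CPAP, long-term oxygen, two or more exacerbations in follow-up, FEV1, BMI, BODE and Charlson. Country and centre are not among them.

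Each factor is first screened in a model with study group at level 0.10. Those that pass go into a multiple-factor model with backward elimination at 0.10, and whatever remains is named an independent predictor. The list may be extended only if the two study groups turn out to be imbalanced on a factor.

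Three other places bear on site:
- Section 6.D says that "hospitalisation may be considered as a potentially biased outcome measure, because somewhat subjective, and physician- or centre-dependent".
- Section 5.A.3 says: "Oxygen prescriptions to the study patients will follow the standard protocols of the investigational centres".
- Section 6.A.2.5 has FEV1 % predicted reported against the reference values each centre uses. Section 6.A.2.6 carries that figure into BODE.

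The protocol also stratifies randomisation by centre (sections 4.A and 4.B.2). It declares everything except the primary analysis exploratory, descriptive and not open to causal interpretation (section 7.B).

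**The concern.** On the protocol's own account, site influences the outcome (the decision to admit) and also some of the candidate predictors (oxygen prescription, FEV1 % predicted, BODE). A model that omits site can attribute site differences in hospital days to those predictors. A true predictor can also be masked if the site differences run the other way.

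The route for extending the list does not help. Because randomisation is by centre, site should be balanced between the arms, so the trigger (imbalance between study groups) would not be expected to bring it in. The group-by-country analysis of variance and the by-country repeats of the Wilcoxon test do not adjust any patient-level factor either.

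At stake is the meaning of the predictor findings. Readers will take an independent predictor to be a characteristic of the patient, and randomisation does not protect these associations. The same applies to hospital days due to severe exacerbations, because section 7.B.3.5 gives that criterion the same set of analyses, including the additional ones.

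**Working it through.** **The plan's own figures.** Section 7.B.2 gives "an expected difference of 10 days of hospitalisation", "an estimated common standard deviation of 25 days", two-sided alpha 0.05 and "power equal to 0.90". The standardised difference is 10/25 = 0.4, so P(X<Y) = Φ(0.4/√2) = 0.6114. Noether's formula gives (1.960 + 1.282)² / [6 × (0.6114 − 0.5)²] ≈ 141.2, or 142 per group against the stated 143. Then 143/(1 − 0.0625) = 152.5, or 153 per group and 306 in total. The sample size reproduces and is not in dispute. It supplies N = 306 and SD = 25 for the check below.

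**Assumptions.** The documents give no between-country or between-centre figures, so these are assumed:
- four countries of equal size, with 1:1 allocation within each;
- overall mean 16 days;
- country means evenly spaced over a range D;
- a binary candidate with overall prevalence 50% and country prevalences evenly spaced over a range P in the same order;
- no effect of the candidate within any country.

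**Formula.** Place the countries at −1, −1/3, 1/3 and 1. The mean square of these positions is (1 + 1/9 + 1/9 + 1)/4 = 0.556. The variance of the candidate is 0.25. Without country in the model, the spurious difference in days is

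(D/2) × (P/2) × 0.556 / 0.25.

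Its standard error is about 2 × SD/√306.

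- D = 10, P = 0.6: 5 × 0.3 × 0.556/0.25 = 3.33 days. The residual SD is about 25.2, so the standard error is about 2.88 and z = 1.16. The chance of passing a two-sided 0.10 test is about 31–32%.
- D = 5, P = 0.6: 2.5 × 0.3 × 0.556/0.25 = 1.67 days, standard error about 2.87, z = 0.58, chance about 16%.
- D = 15, P = 0.6: 7.5 × 0.3 × 0.556/0.25 = 5.0 days, standard error about 2.92, z = 1.71, chance about 53%.

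**Simulation.** There were 2,000 runs per cell, testing the candidate at 0.10 with study group in the model. Each cell shows normal / skewed (gamma) outcome, without country in the model:

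| Range of country means | Prevalence range 20 points | 40 points | 60 points |
|---|---|---|---|
| 0 days | 9.4% / 9.2% | 10.1% / 9.3% | 9.6% / 9.9% |
| 5 days | 9.4% / 10.3% | 11.5% / 13.0% | 15.1% / 16.6% |
| 10 days | 12.0% / 11.9% | 19.7% / 20.0% | 32.4% / 29.9% |
| 15 days | 15.3% / 14.5% | 30.0% / 29.3% | 54.0% / 50.2% |

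With country in the model, every cell lies between 9% and 11%. The study-group test, run at 5% with the candidate in the model but not country, rejected in 3.3% to 5.8% of runs, so it is not inflated.

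A second simulation used negative-binomial days with mean 15 and 3,000 runs per scenario. Without and with country it gave:
- 12% and 10% (country means 0.8–1.2 times average, prevalence 35–65%);
- 35% and 10% (0.6–1.5 times, 30–75%);
- 56% and 10% (0.5–1.5 times, 20–80%).

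Both simulations cover one candidate at the screening step. Survival through backward elimination alongside other factors was not simulated.

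**The case against.** The other side has five good arguments.

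1. **Centre, not country.** The cited sections speak of physicians and centres. None says that admission or prescribing differs by country. That part is an inference from centres being nested in four national health systems. It stands, and with about 45 centres, country terms alone would leave centre differences within a country untouched. The remedy therefore has to include centre.
2. **Only some candidates.** The text supports site dependence for oxygen prescription, FEV1 % predicted and BODE. It says nothing of the kind for CPAP, NIV, age, gender, BMI, smoking or Charlson. This stands.
3. **The large rates need large contrasts.** Rates of 50% or more need country means 15 days apart, more than the 10-day effect the trial is powered for, together with a 60-point prevalence range. No figure in the protocol makes that likelier than a small contrast. This stands, and the size must be given as a range.
4. **Exploratory and non-causal.** Section 7.B says so, and no confirmatory conclusion rests on this model. That lowers the weight of the point but does not remove it. Calling a predictor independent claims adjustment for other determinants, and the model omits one that section 6.D itself describes.
5. **Left to the statistical analysis plan.** A site term could be added there. But the protocol already fixes the list, the thresholds and the label, so this is a choice it has made.

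A reader might go further and infer that country confounding is established, that every candidate is affected, or that the trial's main comparison is biased. The documents support none of these. The first is inferred and the second goes beyond the cited text. The third is contradicted by randomisation within centre and by the study-group results above. Nor is this the only model with several factors: the analysis of variance beside it includes country, though no patient-level predictor.

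**Conclusion.** The omission is real, and its consequence is limited. Site, and by inference country, may confound the associations of oxygen/LTOT, FEV1 and BODE with hospital days, so a factor that only marks a site can end up labelled an independent predictor.

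How often is unknown. It depends on how far hospital days and predictor prevalence differ together between sites, which the protocol does not say. With little variation between countries the effect is negligible to modest; with wide variation in both, the false-selection rate at the screen can reach five times nominal. In every assumed country scenario, adding country restores the nominal rate. The simulations say nothing about centre differences within a country.

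This bears on how the predictor findings may be described. It is no objection to the primary analysis or to the estimated effect of the programme. It is worth correcting because the correction is cheap and the protocol already treats country as a factor of hospital days in the neighbouring analysis of variance.

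**What to change.** In section 7.B.3.5, add site to the exploratory regression as an adjustment term that is always kept:

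- country as a fixed factor in every two-factor screening model and in the multiple-factor model, not subject to backward elimination;
- centre as a random effect in the same models where it can be estimated, since the protocol's own evidence is at centre level;
- the same rule for hospital days due to severe exacerbations.

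State with the results that the analysis is exploratory, as section 7.B already requires.

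The cost is about 3 degrees of freedom for four countries plus one variance component, and a line or two of text. Centre is a randomisation stratum and country is already used in the analysis of variance, so no new data are needed. With about 45 centres sharing some 306 patients (306/45 ≈ 7 each), the centre variance may be poorly estimated. If so, country should stay in and the limitation should be reported.

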## **ANALYSES OF THE SECONDARY EFFICACY CRITERIA**

All analyses of the secondary efficacy criteria will be performed on the ITT data set (*defined in section 7.B.3.1*).

**The number of hospital days due to severe COPD exacerbations** will be analysed in exactly the same way as the primary efficacy criterion, including its primary, supportive and additional analyses previously described.

**The number of moderate and severe COPD exacerbations** separately as recorded by the investigators will be compared between both study groups with the Wilcoxon's rank sum test, in all countries pooled together.

**Time to first severe COPD exacerbation** (*expressed in number of days*) throughout the *Follow-Up Period* will be tabulated by study group, as quantitative data, in the subgroup of patients from the ITT data set experiencing at least one severe COPD exacerbation during their *Follow-Up Period*, as reported by the investigators, in all countries pooled together. Moreover, time to first severe COPD exacerbation throughout the *Follow-Up Period* will be described globally by study group, on the ITT data set, using Kaplan-Meier's estimates to display the probability of survival and of experiencing severe COPD exacerbation. Survival times will be censored at the earliest time of occurrence of the following events:

- the patients' last contact (*this will apply to the subgroup of patients who never experience any severe COPD exacerbation and who are never hospitalised for any reason during their Follow-Up Period*),
- the time to first severe COPD exacerbation (*for the subgroup of patients experiencing at least one severe COPD exacerbation during their Follow-Up Period*),
- the time to first hospital admission for another reason than COPD exacerbation (*for the subgroup of patients hospitalised at least once during their Follow-Up Period*),
- the time to death for another reason than COPD exacerbation, if applicable.

If relevant, time to first severe COPD exacerbation will be compared between both study groups with the Log rank test.

**The use of health care services due to COPD and to all causes** separately will be tabulated by study group and type or unit of time (*i.e., qualitatively in terms of volume without being priced*). Each category separately will be compared between both study groups using either the Student's t test or the Wilcoxon's rank sum test depending on their distribution.

**SGRQ-C total score and component subscores:** quantitative descriptive statistics of the SGRQ-C total score and of each of its three (3) component subscores (*symptoms, activity and impacts*) will be tabulated by study group and visit, using the observed case approach. The absolute variations "*post-Run-In Period – baseline (self-evaluated prior to Visit 1)*" will also be tabulated by study group and visit, for each score and subscore separately.

Moreover, to visualise the evolution of each score and subscore separately, arithmetic means of each score and their 95.0% confidence intervals will be represented graphically (*the x-axis being the assessment time-axis and the y-axis being the arithmetic mean-axis*) with both study groups being represented separately on the same graph, using the observed case approach.

An analysis over time of the mean profile of the SGRQ-C total score and of each of its subscores separately will be performed within a mixed model to deal with patients followed-up over different duration, using the MIXED procedure of the current version of the SAS® software and type III sums of squares. The global parametric analysis of covariance model on repeated measurements used will include the following factors:

- score assessed during the *Run-In Period* as covariate,
- study group and visit as fixed factors,
- interaction between study group and visit and interaction between study group and score assessed during the *Run-In Period (i.e., the covariate)* as fixed factors,
- patient as random factor.

In a first step, the best structure of the variance-covariance matrix will be identified using the Akaike's Information Criterion (AIC), which is based on the Restricted Maximum Likelihood (REML) and the number of covariance parameters. The model with the AIC lowest value will be considered as the best one. In a second step, inference will be drawn about fixed effects in the frame of the model with the best structure of the variance-covariance matrix selected in the first step.

When relevant, appropriate contrasts will be calculated and the associated confidence intervals will be displayed. In case of a statistically significant interaction evidenced at level  $\alpha = 0.10$ , further separate parametric analyses of variance may be carried out, if appropriate and potentially relevant from a clinical point of view.

**15D health-related quality of life instrument:** the 15D score will be tabulated over time, analysed and represented graphically in exactly the same way as the SGRQ-C total score.

**Pulmonary function tests parameters:** for each spirometry parameter recorded by the investigators (*as listed in section 6.A.2.5*), separately, quantitative descriptive statistics will be tabulated by study group and visit, using the observed case approach.

For each spirometry parameter assessed, separate global parametric analyses of covariance on Visit 5 (*Month 12 or study end in case of premature withdrawal*) measurements will also be performed using a mixed model, including the following factors:

- the corresponding spirometry parameter measured during the *Run-In Period* as covariate,
- study group as fixed factor,
- interaction between study group and corresponding spirometry parameter measured during the *Run-In Period* (*i.e., the covariate*) as fixed factor,
- patient as random factor.

**Six-Minute Walking Distance (6MWD) and related parameters:** the 6MWD will be tabulated using quantitative descriptive statistics, by study group, visit and conditions of assessment (*i.e., either on room air or on oxygen*), using the observed case approach.

Moreover, in the subgroup of patients having performed their 6MWTs in the same conditions at Visits 1 and 5, a global parametric analysis of covariance of the 6MWD assessed on Visit 5 will be performed using a mixed model including the following factors:

- the 6MWD assessed during the *Run-In Period* as covariate,
- study group and conditions of assessment as fixed factors,
- interaction between study group and 6MWD assessed during the *Run-In Period* (*i.e., the covariate*) and interaction between study group and conditions of assessment as fixed factors,
- patient as random factor.

The other parameters recorded during each 6MWT performed (*as listed in section 6.A.2.5*) will only be tabulated using descriptive statistics, by study group, visit and conditions of assessment, using the observed case approach.

**Transthoracic Doppler echocardiography parameters:** for each transthoracic Doppler echocardiography parameter recorded by the investigators or calculated by the e-CRF (*as listed in section 6.A.2.5*), separately, quantitative descriptive statistics will be tabulated by study group and visit, using the observed case approach.

For each parameter, separate global parametric analyses of covariance on Visit 5 measurements will also be performed using the same model as the one described for the pulmonary function tests, the corresponding transthoracic Doppler echocardiography parameter measured during the *Run-In Period* being the covariate of the analysis model.

**BODE index:** the BODE index will be tabulated by study group and visit, using the observed case approach, as both quantitative and categorical data (*using the four (4) categories mentioned in section 6.A.2.6, i.e., [0 ; 2], [3 ; 4], [5 ; 6] and [7 ; 10]*).

Moreover, a global parametric analysis of covariance on Visit 5 measurements will be performed using the same model as the one described for the pulmonary function tests, the BODE index assessed during the *Run-In Period* being the covariate of the analysis model.

**Hospital Anxiety and Depression Scale (HADS) scores:** the HAD-D and HAD-A scores calculated by using the algorithm provided by their owner will be tabulated separately over time, analysed and represented graphically in exactly the same way as the SGRQ-C total score.

Moreover, at each visit separately, the number and percentage of patients presenting a HAD-D score  $\geq 8$ , as well the number and percentage of patients presenting a HAD-A score  $\geq 8$  will be tabulated separately, by study group.

**Prescription of oxygen therapy:** over the *Follow-Up Period*, the number and percentage of patients for whom oxygen therapy is implemented (*while the patient was not on oxygen therapy at Selection*) will be tabulated descriptively by study group. The concerned patients will be further described by study group regarding their time to onset of oxygen therapy and criteria for prescription. If relevant, time to onset of oxygen therapy (*expressed in number of days*) throughout the *Follow-Up Period* will be described by study group, using Kaplan-Meier's estimates, and it will be compared between both groups with the Log rank test.

If relevant, these descriptions will be repeated to highlight the onset of the prescriptions of continuous Long Term Oxygen Therapy (*LTOT, i.e., the start of daily oxygen duration prescribed of 15 hours or more*) over the *Follow-Up Period*.

In the subgroup of patients on oxygen therapy at Selection and/or during their study participation and on the period of their oxygen prescription overlapping their holding of the *NOWOX* device, the average daily duration prescribed will be tabulated by study group. For each patient for whom a change in the daily duration of oxygen prescription is recorded throughout the *Follow-Up Period*, the individual daily duration of oxygen prescription will be estimated by using the sum of all recorded daily durations prescribed multiplied by the number of days of the corresponding prescription, divided by the total number of days on oxygen therapy. In case of missing or incomplete information necessitating monthly approximation in this average calculation, it will be considered that each month lasts 30.5 days.

**Compliance to oxygen therapy:** in the subgroup of patients on oxygen therapy at Selection and/or during their study participation and on the period of their oxygen prescription overlapping their holding of the *NOWOX* device, the average daily use of oxygen therapy over 24 hours, as well as the average use of oxygen therapy at night (*i.e., over the time interval [22:00 ; 6:00]*) and the average use of oxygen therapy during the day (*i.e., over the time interval [06:00 ; 22:00]*) will be calculated separately over at most eight (8) successive periods (*for the first patients included in the study who have been followed up 24 months*) defined by the scheduled visits of the patients at the investigational centre, without taking into account the recordings collected by the *NOWOX* device on the day of each actual visit, *i.e.,* when applicable, over the successive periods:

- between the day following the actual date of Visit 1 and the day preceding the actual date of Visit 2 (*both included*) (*period 1*),
- between the day following the actual date of Visit 2 and the day preceding the actual date of Visit 3 (*both included*) (*period 2*),
- ... and so on, up to the last period between the day following the actual date of Visit 8 and the day preceding the actual date of Visit 9 (*both included*) (*period 8, if applicable*).

The average daily use of oxygen therapy and its two (2) components at night and during the day separately, will be tabulated by study group, over each period separately, using quantitative descriptive statistics. These tabulations, as well as their graphical representations and analyses over time described below will be performed twice in the subgroup of patients on oxygen therapy at any time throughout their study participation and on the period of their oxygen prescription overlapping their holding of the *NOWOX* device: first, on all recordings collected by the *NOWOX* device for all patients constituting the ITT data set, and second, on the recordings collected on the days when patients from the ITT data set are not on any concomitant respiratory assistance (*i.e. Continuous Positive Airway Pressure (CPAP) therapy and/or home Non-Invasive Ventilation (NIV)*) as reported by the investigators. They will be repeated in a second step in the subgroup of patients on continuous LTOT (*i.e., with daily oxygen duration prescribed of 15 hours or more*) at any time throughout their study participation and on the period of their LTOT prescription overlapping their holding of the *NOWOX* device.

Moreover, to visualise the evolution of the recordings, arithmetic means of each average daily use of oxygen therapy calculated separately and their 95.0% confidence intervals will be represented graphically (*the x-axis being the period-axis and the y-axis being the arithmetic mean-axis*) with both study groups being represented separately on the same graph.

An analysis over time of the mean profile of the average daily use of oxygen therapy and its two (2) components separately will be performed within a mixed model to deal with patients followed-up over different duration, using the MIXED procedure of the current version of the SAS® software and type III sums of squares. The global parametric analysis of variance model on repeated measurements used will include the following factors:

- study group and period of evaluation as fixed factors,
- interaction between the study group and the period of evaluation as fixed factor,
- patient as random factor.

In a first step, the best structure of the variance-covariance matrix will be identified using the Akaike's Information Criterion (AIC), which is based on the Restricted Maximum Likelihood (REML) and the number of variance parameters. The model with the AIC lowest value will be considered as the best one. In a second step, inference will be drawn about fixed effects in the frame of the model with the best structure of the variance-covariance matrix selected in the first step.

When relevant, appropriate contrasts will be calculated and the associated confidence intervals will be displayed. In case of a statistically significant interaction evidenced at level  $\alpha = 0.10$ , further separate parametric analyses of variance may be carried out, if appropriate and potentially relevant from a clinical point of view.

Moreover, to explore further the collected data, the average daily use of oxygen therapy and its two (2) components separately will be calculated separately over the first week (*i.e., the first 7 days*) following each patient's visit at the investigational centre (*from the day following the actual date of Visit 1 onwards*) and over the last week (*i.e., the last 7 days*) preceding each patient's visit at the investigational centre (*from the last 7 days preceding the actual date of Visit 2 onwards*), without taking into account the recordings collected by the *NOWOX* device on the day of each actual visit. These weekly means will be tabulated by study group, over each 7-day period separately, using quantitative descriptive statistics. The pre-investigational centre visit weekly means and the post-investigational centre visit weekly means separately will be represented graphically and analysed in the same way as the quarterly means of the daily use of oxygen therapy previously described.

Additionally, for each unscheduled hospitalisation separately, the average daily use of oxygen therapy and its two (2) components separately will be calculated separately over the week (*i.e., the 7 days*) preceding each unscheduled hospital admission and over the week (*i.e., the 7 days*) following each unscheduled hospital discharge, without taking into account the recordings collected by the *NOWOX* device on the days of hospital admission and discharge. These weekly means will be tabulated by study group and sequential number of hospitalisation, over each 7-day period separately, using quantitative descriptive statistics. No statistical test will be performed.

In the subgroup of patients on oxygen therapy at Selection and/or during their study participation and on the period of their oxygen prescription overlapping their holding of the *NOWOX* device, for each patient and each day on oxygen prescription, the relative difference ‘ $100 \times (\text{daily use of oxygen therapy over 24 hours as estimated by the } NOWOX \text{ device} - \text{corresponding individual daily duration of oxygen prescription } (D_{O2 \text{ prescribed}})) / D_{O2 \text{ prescribed}}$ ’ will be calculated, as well as the absolute difference ‘ $\text{daily use of oxygen therapy over 24 hours as estimated by the } NOWOX \text{ device} - \text{corresponding individual daily duration of oxygen prescription } (D_{O2 \text{ prescribed}})$ ’.

